8.3.2. Method of Detecting AEs and SAEs

The method of recording, evaluating, and assessing causality of AEs and SAEs and the procedures for completing and transmitting SAE reports are provided in [Appendix 10.3](#).

Care will be taken not to introduce bias when detecting AEs and/or SAEs. Open-ended and nonleading verbal questioning of the subject is the preferred method to inquire about AE occurrences.

8.3.3. Follow-up of AEs and SAEs

After the initial AE/SAE report, the Investigator is required to proactively follow each subject at subsequent visits/contacts. All SAEs, will be followed until resolution, stabilization, the event is otherwise explained, or the subject is lost to follow-up (as defined in [Section 7.4](#)). Further information on follow-up procedures is provided in [Appendix 10.3](#).

8.3.4. Regulatory Reporting Requirements for SAEs

- Prompt notification by the Investigator to the Sponsor of a SAE is essential so that legal obligations and ethical responsibilities towards the safety of subjects and the safety of a study drug under clinical investigation are met.
- The Sponsor has a legal responsibility to notify both the local regulatory authority and other regulatory agencies about the safety of a study drug under clinical investigation. The Sponsor will comply with country-specific regulatory requirements relating to safety reporting to the regulatory authority, Institutional Review Boards (IRB)/Independent Ethics Committees (IEC), and Investigators.
- For all studies must be prepared for suspected unexpected serious adverse reactions (SUSAR) according to local regulatory requirements and Sponsor policy and forwarded to Investigators as necessary.
- An Investigator who receives an Investigator safety report describing a SAE or other specific safety information (e.g., summary or listing of SAEs) from the Sponsor will review and then file it along with the IB and will notify the IRB/IEC, if appropriate according to local requirements.

8.3.5. Pregnancy

- Details of all pregnancies in female subjects and of female partners of male subjects will be collected as outlined in [Section 10.4](#) (Appendix 4).
- If a pregnancy is reported, the Investigator should inform the Sponsor within 24 hours of learning of the pregnancy and should follow the procedures outlined in [Appendix 4](#).
- Abnormal pregnancy outcomes (e.g., spontaneous abortion, fetal death, stillbirth, congenital anomalies, ectopic pregnancy) are considered SAEs.

8.3.6. Deaths

All deaths will be recorded in the eCRF. As deaths are always considered SAEs, they should be reported to the Sponsor within 24 hours of site awareness.

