3. OBJECTIVES AND ENDPOINTS

Objectives	Endpoints
Primary	

 To evaluate clinical benefit of BLD-2660 in hospitalized adults with recently diagnosed SARS-CoV-2 infection 	
 Time to recovery as defined by no longer requiring oxygen support or hospital discharge, whichever occurs first

 To evaluate improvement in oxygenation in hospitalized adults with COVID-19 treated with BLD-2660 	
 Change from baseline to Day 10 or hospital discharge, if sooner, in the ratio of peripheral hemoglobin oxygen saturation to fraction of inspired oxygen (SpO₂/FiO₂)
Secondary	

 To evaluate the safety and tolerability of BLD-2660 in the same population 	
 Incidence of TEAEs and serious adverse events (SAEs)

 To evaluate improvement in oxygenation 	
 Improvement from baseline to Days 10, 14, 21 and 28 as measured by the ratio of hemoglobin oxygen saturation to inspired oxygen fraction (SpO₂/FiO₂), categorized on the 4-point ordinal scale (Table 4) Time to discontinuation of oxygen supplementation requirement Mean SpO₂ for subjects not requiring oxygen supplementation at Days 5, 10, 21 and 28 Number of O₂ supplementation free days during hospitalization Proportion of subjects who do not require oxygen supplementation (sustained for at least 24 hours) during hospitalization 
Note, criteria for removal of oxygen supplementation is defined as resting (5 minutes of rest) room air saturation >90%

Objectives	Endpoints

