8.3.1. Time Period and Frequency for Collecting AE and SAE Information

[Table 7](#) below summarizes the different reporting periods for AEs and SAEs.

Table 7: Adverse Event Reporting Periods

Type of Event	Adverse Event	Serious Adverse Event
Reporting period	From consent until Day 28 visit (at least 18 days after last dose of study drug).	From consent until Day 28 visit (at least 18 days after the last dose of study drug). SAEs will be recorded for study drug and for remdesivir.
Reporting Timelines to the Sponsor	Entered into the clinical database on an ongoing basis	Within 24 hours of site awareness

Medical occurrences that begin before the start of study drug but after obtaining informed consent will be recorded on the Adverse Events section of the case report form (CRF) and will be identified in the analysis as non-treatment-emergent adverse events (non-TEAEs).

All SAEs (for study drug and for remdesivir) will be recorded and reported to the Sponsor or designee immediately and under no circumstance should this exceed 24 hours from site awareness, as indicated in Appendix 3 ([Section 10.3](#)). The Investigator will submit any updated SAE data to the Sponsor or designee within 24 hours of it being available.

Investigators are not obligated to actively seek AEs or SAEs after conclusion of the study participation. However, if the Investigator learns of any SAE, including a death, at any time after a subject has been discharged from the study, and he/she considers the event to be related to the study drug or study participation, the Investigator must promptly notify the Sponsor or designee.

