10.3.1. Definition of AE

AE Definition

 • An AE is any untoward medical occurrence in a patient or clinical study subject, temporally associated with the use of study drug, whether or not considered related to the study drug. • NOTE: An AE can therefore be any unfavorable and unintended sign (including an abnormal laboratory finding), symptom, or disease (new or exacerbated) temporally associated with the use of study drug.

Events Meeting the AE Definition

 • Any abnormal laboratory test results (hematology, clinical chemistry, or urinalysis) or other safety assessments (e.g., ECG, radiological scans, vital signs measurements), including those that worsen from baseline (see bullet below), considered clinically significant in the medical and scientific judgment of the Investigator (i.e., not related to progression of underlying disease). • Exacerbation of a chronic or intermittent pre-existing condition including either an increase in frequency and/or intensity of the condition. • New conditions detected or diagnosed after study drug administration even though it may have been present before the start of the study. • Signs, symptoms, or the clinical sequelae of a suspected drug-drug interaction. • Signs, symptoms, or the clinical sequelae of a suspected overdose of either study drug or a concomitant medication. Overdose per se will not be reported as an AE/SAE unless it is an intentional overdose taken with possible suicidal/self-harming intent. Such overdoses should be reported regardless of sequelae.

Events NOT Meeting the AE Definition

 • Any clinically significant abnormal laboratory findings or other abnormal safety assessments which are associated with the underlying disease, unless judged by the Investigator to be more severe than expected for the subject's condition. • The disease/disorder being studied or expected progression, signs, or symptoms of the disease/disorder being studied, unless more severe than expected for the subject's condition.

- Medical or surgical procedure (e.g., endoscopy, appendectomy): the condition that leads to the procedure is the AE.
- Situations in which an untoward medical occurrence did not occur (social and/or convenience admission to a hospital).
- Anticipated day-to-day fluctuations of pre-existing disease(s) or condition(s) present or detected at the start of the study that do not worsen.

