10.3.2. Definition of SAE

If an event is not an AE per definition above, then it cannot be an SAE even if serious conditions are met (e.g., hospitalization for signs/symptoms of the disease under study, death due to progression of disease).

A SAE is defined as any untoward medical occurrence that, at any dose:
Results in death
Is life-threatening The term 'life-threatening' in the definition of 'serious' refers to an event in which the subject was at risk of death at the time of the event. It does not refer to an event which hypothetically might have caused death, if it were more severe.
Requires inpatient hospitalization or prolongation of existing hospitalization 
 • In general, hospitalization signifies that the subject has been detained (usually involving at least an overnight stay) at the hospital or emergency ward for observation and/or treatment that would not have been appropriate in the physician's office or outpatient setting. Complications that occur during hospitalization are AEs. If a complication prolongs hospitalization or fulfills any other serious criteria, the event is serious. When in doubt as to whether "hospitalization" occurred or was necessary, the AE should be considered serious. • Hospitalization for elective treatment of a pre-existing condition that did not worsen from baseline is not considered an AE.
Results in persistent disability/incapacity 
 • The term disability means a substantial disruption of a person's ability to conduct normal life functions. • This definition is not intended to include experiences of relatively minor medical significance such as uncomplicated headache, nausea, vomiting, diarrhea, influenza, and accidental trauma (e.g., sprained ankle) which may interfere with or prevent everyday life functions but do not constitute a substantial disruption.
Is a congenital anomaly/birth defect

Other situations:

- Medical or scientific judgment should be exercised in deciding whether SAE reporting is appropriate in other situations such as important medical events that may not be immediately life-threatening or result in death or hospitalization but may jeopardize the subject or may require medical or surgical drug to prevent one of the other outcomes listed in the above definition. These events should usually be considered serious.

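### For deaths judged to be expected COVID-19 progression, protocol 8.3.6 makes them SAEs and Appendix 3 says they cannot be, so SAE counts and 24-hour reports depend on which rule a site follows

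*Protocol*

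**What the plan says.** Protocol 8.3.6 has two sentences. The first covers capture: "All deaths will be recorded in the eCRF". The second covers status and timing: "As deaths are always considered SAEs, they should be reported to the Sponsor within 24 hours of site awareness". It names no exception.

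Appendix 3 is more restrictive. Among events that do not meet the AE definition, protocol 10.3.1 lists: "The disease/disorder being studied or expected progression, signs, or symptoms of the disease/disorder being studied, unless more severe than expected" for the subject's condition. Protocol 10.3.2 then states: "If an event is not an AE per definition above, then it cannot be an SAE even if serious conditions are met". Its examples include "death due to progression of disease".

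The main text points sites to Appendix 3. Section 8.3 refers there for the AE and SAE definitions. Section 8.3.1 requires SAEs to be reported "immediately and under no circumstance should this exceed 24 hours from site awareness" and cites the same appendix.

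SAE incidence is a secondary safety endpoint in protocol section 3 and SAP 1.1. SAP 5.8.2 tabulates TEAEs by CTCAE grade (including Grade 5) and serious TEAEs, by treatment group. It gives no rule for deaths attributed to disease progression.

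**The concern.** One sentence makes all deaths SAEs, and another says that some deaths cannot be SAEs. A site following 8.3.6 would file an SAE within 24 hours for a death from expected COVID-19 progression. A site following Appendix 3 would find that the same death is not an AE, and so is neither an SAE nor subject to the SAE clock.

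Two things are at stake. The first is the meaning of a listed secondary endpoint: SAE incidence by arm would mix two definitions, and the Grade 5 TEAE row would be affected too, because a death ruled out as an AE leaves all the TEAE tables. The second is prompt notice to the Sponsor. Protocol 7.1 sets no stopping rules for the study as a whole and relies instead on Sponsor oversight and DMC safety reviews, so uniform reporting of deaths has some weight.

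**Working it through.** The documents state no figure for this point, so there is none to reproduce. The check compares the two rules by type of death, looks for a clause that settles them, and then gives a sense of scale.

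**1. The two rules side by side**

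| Type of death | Protocol 8.3.6 | Protocol 10.3.1 with 10.3.2 |
|---|---|---|
| Cause other than COVID-19, meeting the AE definition | SAE, 24-hour report | SAE (fatal AE) |
| COVID-19 progression judged more severe than expected | SAE, 24-hour report | AE under the exception in 10.3.1, so SAE |
| COVID-19 progression judged as expected | SAE, 24-hour report | Not an AE, so not an SAE |

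The rules conflict only in the third row. The example in 10.3.2 has no qualifier and, read alone, would cover the second row as well. But its sentence works through the AE definition, and that definition keeps the second row in. Placing a death in row two or row three is the investigator's judgement, which adds variation between sites.

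**2. Search for a reconciling clause**

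Protocol 8.3, 8.3.1, 8.3.4 and Appendix 3, and SAP 5.8.2, contain no statement that one rule prevails. SAP section 1 says that the SAP overrides the protocol where they differ, but the SAP is silent here. Both texts are in the body of the current protocol, not in the amendment log.

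**3. What varies and what does not**

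- Varies, for row-three deaths: the SAE count, the Grade 5 TEAE count, and whether a 24-hour report to the Sponsor is due.
- Does not vary: recording of the death in the eCRF (protocol 8.3.6), and survival status at Days 14, 21 and 28 and the post-study visit (protocol 1.2). Score 6 on the ordinal scale (protocol Table 5, analysed in SAP 5.6.2) and death as a reason for discontinuation (protocol 7.2 and 7.3, reported under SAP 5.4) also stay the same.

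**4. Scale only**

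Inputs: 120 planned subjects, 80 active and 40 control (protocol 9.2), and background fatality in hospitalized patients of 14%, 95% CI 6.2 to 21.5% (protocol 2.2). Applying that rate to this trial is an assumption. Expected deaths = number of subjects × rate.

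| Rate | All 120 | Active 80 | Control 40 |
|---|---|---|---|
| 6.2% | 7.4 | 5.0 | 2.5 |
| 14% | 16.8 | 11.2 | 5.6 |
| 21.5% | 25.8 | 17.2 | 8.6 |

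Chance of at least one death at the lowest rate: 1 − (1 − 0.062)^120 = 0.9995. Deaths are therefore to be expected if any rate in this range applies.

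The documents do not give the share of deaths due to progression, so the disputed number runs from 0 to all deaths. At 14%, the upper bound on the shift in SAE incidence is 16.8/120 = 14 percentage points. It is reached only if every death falls in row three and none of those subjects had another SAE.

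**The case against.** The strongest reply is that the conflict is narrow and loses no data. Section 8.3.6 is the only section specifically about deaths, and it plainly tells sites to report them. Section 10.3.2 is a definition and does not tell anyone to withhold a report. The eligibility criteria exclude subjects on FiO2 of 0.75 or more and those requiring or expected to require mechanical ventilation, so an investigator could well judge a death more severe than expected, which moves it out of dispute. Safety analyses are descriptive (SAP 5.8). All of this stands. It limits the size of the problem but does not remove the contradiction.

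Several stronger readings are tempting, and the documents do not support them:

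- *Appendix 3 removes all COVID-19 deaths, and these are most of the deaths.* The exception in 10.3.1 keeps some of them in, and neither document says what share is due to progression.
- *With the 28-day mortality endpoint missing from the SAP's list, deaths are hidden if they are not SAEs.* They also reach by-arm outputs through the ordinal scale and disposition. These are not a clean substitute, since the SAP gives no rule for carrying score 6 forward to later visits, but deaths are not lost.
- *Regulatory reports will be missed.* The report in question is the 24-hour one to the Sponsor. SUSAR reporting (protocol 8.3.4) needs a suspected, unexpected reaction, which a death attributed to expected progression would rarely be under either rule. That any site will in fact report late is a risk, not something that the documents show.
- *The DMC depends on SAE reports to learn of deaths.* Protocol 9.5.1 says only that it reviews safety results, and SAP 5.10 says that its interim review also included efficacy data.

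**Conclusion.** The contradiction is real but confined to deaths judged to be expected progression of COVID-19. For those deaths the protocol gives two incompatible instructions, and SAE incidence, Grade 5 TEAE counts and the duty to notify the Sponsor within 24 hours follow whichever a site applied. The number affected is unknown. Any figure rests on two assumptions: that a fatality rate for hospitalized patients in general carries over to this selected population, and some value for the share of deaths due to progression.

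Classification is made in a double-blind study, so the conflict alone gives no reason to expect an error favouring one arm. What it does is make the counts ambiguous.

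This is an internal inconsistency, not a design choice. It should be fixed, but it touches no primary endpoint, error rate, power figure or randomization step.

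**What to change.** 1. Reconcile protocol 8.3.6 with 10.3.1 and 10.3.2 so that one rule governs the SAE status and Sponsor reporting of deaths, and tell sites. Which rule to adopt is for the sponsor to decide. SAP 5.10 mentions a planned protocol amendment to add a Phase 3 part; the same wording should not carry over into it unresolved.
2. SAP 5.10 says that enrolment has completed, so the practical step for this phase comes before database lock: list every death from the eCRF and survival status, compare it with the AE and SAE records, and query those classified inconsistently. SAP 5.10 also plans an interim analysis for the sponsor before lock, so this is best done by staff who have not seen results by arm.
3. State in SAP 5.8.2 how deaths attributed to progression are counted in the SAE and Grade 5 tables.
4. Add one table of all deaths by arm, whatever their AE or SAE classification.

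The cost is a clarification letter or amendment, one reconciliation listing, a sentence in the SAP and one table from data already being collected.

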8.4. Pharmacokinetics

PK assessment of BLD-2660 will be analyzed using a population PK approach based upon sparse sampling to be obtained at designated timepoints as specified in the SoA ([Section 1.2](#)). Note, if NGT is inserted, PK samples will also be collected 2 hours postdose after the first NGT use.

- Instructions for the collection and handling of biological samples will be provided by the Sponsor. The actual date and time (24-hour clock time) of each sample will be recorded.
- Samples will be used to evaluate the PK of BLD-2660. Samples collected for analyses of BLD-2660 serum concentration may also be used to evaluate safety, efficacy and/or pharmacodynamic aspects related to concerns or questions arising during or after the study.
- Subject confidentiality will be maintained. At visits during which blood samples for the determination of PK, and PD related to BLD-2660 will be taken, 1 sample of sufficient volume can be used.
- Any changes in the timing or addition of time points for any planned study assessments must be documented and approved by the relevant study team member and then archived in the Sponsor and site study files but will not constitute a protocol amendment. The IRB/IEC will be informed of any safety issues that require alteration of the safety monitoring scheme or amendment of the ICF.

8.5. Pharmacodynamics and Biomarker Assessments

Blood samples will be collected and analyzed for biomarker analysis as specified in the SoA ([Section 1.2](#)) including IL-6 and D-dimers. Additional blood sample for future biomarker analyses will also be collected and stored.

The Sponsor or designee will supply complete written instructions for handling, processing, storage, and shipping of biomarker samples in the Laboratory Manual.

Samples may be stored for a maximum of 15 years after the last subject's last visit for the study, at a facility selected by the Sponsor, to enable further analysis of biomarker responses to BLD2660.

9. STATISTICAL CONSIDERATIONS

9.1. Statistical Hypothesis

Two primary hypotheses will be tested. The study will be declared a success if either of the hypotheses are statistically significant.

Hypothesis 1: Will evaluate clinical benefit in hospitalized adult subjects with recent SARS-CoV-2 infection. The primary endpoint is time to recovery as defined by no longer requiring oxygen support or hospital discharge, whichever occurs first. The null hypothesis is the hazard ratio is = 1 and the alternative hypothesis is the hazard ratio does not equal 1.

Hypothesis 2: Will evaluate improvement in oxygenation in hospitalized adult subjects with recent SARS-CoV-2 infection at the time of discharge, or Day 10, if they are still hospitalized. The primary endpoint is the change from baseline to Day 10 or hospital discharge if sooner in the ratio of hemoglobin oxygen saturation to inspired oxygen fraction (SpO_2/FiO_2). The null hypothesis is the mean treatment difference equals 0 and the alternative hypothesis is the mean treatment difference does not equal 0.

9.2. Sample Size Determination

Time to clinical improvement

A randomized, double-blind, placebo-control study evaluating remdesivir in 1063 hospitalized patients with COVID-19 reported 606 recoveries, with a median time to recovery of 11 days and 15 days in the remdesivir and placebo groups, respectively (remdesivir package insert). Recovery was defined as the first day on which the subject satisfies one of the following 3 categories from the ordinal scale: 1) Hospitalized, not requiring supplemental oxygen - no longer requires ongoing medical care; 2) Not hospitalized, limitation on activities and/or requiring home oxygen; 3) Not hospitalized, no limitations on activities (<https://clinicaltrials.gov/ct2/show/NCT04280705>).

Assuming the median time to clinical improvement, defined as no longer requiring oxygen support or hospital discharge whichever occurs first, will be 12-15 days in the placebo group, and that at least 75 of the planned 120 subjects enrolled meet the clinically improved criteria, the study will have at least 80% power to detect a 50% reduction in the time to clinical improvement, (i.e., hazard ratio of 0.5).

Change from baseline to Day 10 or hospital discharge if sooner in the ratio of hemoglobin oxygen saturation to inspired oxygen fraction (SpO_2/FiO_2).

A prospective observational cohort study of non-intubated moderate to severe ARDS patients (Ding, 2020) reported the partial pressure of oxygen (PaO_2)/ FiO_2 ratio for 10 patients, which gave a mean and standard deviation of 147 ± 46 mm Hg. Converting to a SpO_2/FiO_2 ratio gives a mean and standard deviation of 192 ± 39 using the equation reported by Rice et al. (2007) (Rice, 2007).

Assuming a standard deviation of 40 in the SpO_2/FiO_2 ratio, a sample size of 120 subjects (80 active, vs 40 control) will provide approximately 90% power to detect a treatment difference in

the SpO₂/FiO₂ ratio of 25 or greater, based on a two-sample t-test with a two-sided 5% significance level

